### **8.6 Alzheimer's Disease Assessment Scale-Cognitive Subscale 11 (ADAS-Cog 11)**

The Alzheimer's Disease Assessment Scale-Cognitive items (ADAS-Cog) is an 11-item scale which has been widely used in AD therapeutic research to assess memory, other cognitive functions and praxis ([Mohs 1988](#)). The ADAS-Cog 11 will be performed by an experienced and trained clinician as the primary endpoint to measure cognitive ability and to evaluate change from Baseline. The ADAS-Cog 11 is to be administered at Screening (Visit 1), Visit 2, Visit 5, Visit 7, Visit 9, Visit 10 (or Early Termination), and Visit 11 (Safety Follow-up Visit). The ADAS-Cog 11 takes approximately 30 minutes to complete.

Open Label Extension: The ADAS-Cog 11 is to be administered at Visits OLE-3, OLE-4, OLE-6 (or Early Termination) and OLE-9 (OLE Safety Follow-up Visit).

**NOTE:** Effective 16 February 2021, the OLE portion of the study was terminated by the Sponsor.

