### **8.8 Alzheimer's Disease Cooperative Study Group-Activities of Daily Living (ADCS-ADL)**

The Alzheimer's Disease Cooperative Study Group-Activities of Daily Living (ADCS-ADL) will be performed to assess the subject's ability to perform activities of daily living and will be administered at Visit 2, Visit 5, Visit 7, Visit 9, Visit 10 (or Early Termination), and Visit 11 (Safety Follow-up Visit). The ADCS-ADL takes approximately 20 to 25 minutes to complete.

Open Label Extension: The ADCS-ADL will be administered at Visits OLE-3, OLE-4, OLE-6 (or Early Termination) and OLE-9 (OLE Safety Follow-up Visit). **NOTE:** Effective 16 February 2021, the OLE portion of the study was terminated by the Sponsor.

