### **11.2 Determination of Sample Size**

The study will have an adaptive design that allows for potential adjustment in sample size and evaluation of efficacy based on the results of a planned interim analysis. An unblinded interim analysis will be conducted by a firewalled independent statistician (all clinical trial personnel will remain blinded) when approximately 100 subjects per arm have completed the Week 24 visit. Approximately 573 subjects are planned to be randomized 1:1:1 per treatment group (191 per treatment group) assuming approximately 10% will drop out prior to 48 weeks. Due to the planned interim analysis, adjustments will be made to the alpha level used in the final analysis to control for overall Type I error. The final criterion for efficacy to be used at the interim and final analysis depends on when the interim analysis occurs. The Lan-DeMets method modified according to [Chen et al. \(2004\)](#) to account for correlation between endpoints used at the interim and final analyses will be used to calculate the level of significance for each analysis. As originally planned, with 573 subjects randomized, an expected 10% discontinuation rate, and a single primary outcome, a total of 172 subjects per treatment group would provide approximately 90% power to detect a 2.5-point difference between the active treatment group compared to placebo with respect to change from baseline on the ADAS-Cog 11, assuming a standard deviation of 7.1, respectively at a significance level (alpha) of 0.05 using a two-sided test. The ADCS-ADL was added as a co-primary outcome, with assumptions of a 3.9-point difference between the active treatment group compared to placebo with respect to change from baseline on ADCS-ADL, assuming a standard deviation of 10.5, providing approximately 95% power on this outcome

measure, with approximately 90% power for the overall co-primary outcomes, depending on their correlation.

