#### **11.3.2 Efficacy Analysis**

##### **11.3.2.1 Primary Efficacy Analysis**

The co-primary endpoints are the mean change from baseline in ADAS-Cog 11 at the end of the study (average of Weeks 40 and 48), and the mean change from baseline in the Alzheimer's Disease Cooperative Study – Activities of Daily Living (ADCS-ADL) at the end of the study (average of Weeks 40 and 48).

Each of the coprimary endpoints will be analyzed using a mixed-effects model for repeated measures (MMRM) with SAS PROC MIXED to compare change from baseline for COR388 HCl vs placebo. The MMRM model will include treatment group, study visit, site/country, treatment group by study visit interaction as fixed effects, and baseline MMSE (average of the last two non-missing assessments

collected prior to or at the day of first dose of the IP), ApoE4 status, and acetylcholinesterase inhibitor and/or memantine usage at baseline as factors with baseline score as a covariate using the ITT population. The analysis will be based on unstructured covariance matrix to model the within-subject errors. A Kenward-Roger approximation will be used for the denominator degrees of freedom.

Summary statistics (n, mean, standard deviation, minimum, median, and maximum) will be presented for the observed values for each of the coprimary endpoints at each time point for the ITT population, including weeks 40 and 48 separate as well as averaged. Summary statistics will also be presented for the change from baseline values to each postbaseline time point as listed above.

The Type I error for the interim and final analysis will be adjusted using the Lan-DeMets spending function. Detailed of the adjustment is presented in [Section 11.3.2.3](#) and in the [SAP](#).

Treatment comparisons of 40 mg and 80 mg COR388 HCl to placebo will be adjusted using Benjamini-Hochberg multiplicity adjustment procedure ([Benjamini and Hochberg, 1995](#) and [Benjamini and Yekutieli, 2001](#)). Both treatment comparisons, 40 mg (low dose) and 80 mg COR388 HCl (high dose) to placebo are considered of equal interest.

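### Two pre-dose ADAS-Cog 11 scores are collected, but the primary model appears to use only one and fits a single baseline slope for all visits

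*Protocol*

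**What the plan says.** Section 11.3.2.1 gives one MMRM for each co-primary endpoint. Its fixed effects are treatment, visit, site/country and treatment by visit. It adds baseline MMSE, ApoE4 status and symptomatic AD medication, the last listed as "usage at baseline as factors with baseline score as a covariate". The same sentence defines the MMSE term precisely: "baseline MMSE (average of the last two non-missing assessments", taken up to the day of first dose. The endpoint's own baseline is not defined further, and the list contains no baseline-by-visit interaction.

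On data collection, Section 8.6 states: "The ADAS-Cog 11 is to be administered at Screening (Visit 1), Visit 2, Visit 5, Visit 7" and later visits. Section 7.2 places the Visit 2 ADAS-Cog 11 before study drug is given, so both scores are pre-dose. CDR-SB follows the same pattern (Section 8.7). ADCS-ADL does not; Section 8.8 says it "will be administered at Visit 2, Visit 5, Visit 7, Visit 9, Visit 10 (or Early Termination), and Visit 11", so it has one pre-dose rating.

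Section 11.3.2.2 carries the primary methodology over to the secondary endpoints, including CDR-SB. Section 11.3.5 makes CDR-SB a co-primary endpoint at the interim analysis.

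**The concern.** A single ADAS-Cog 11 score is the subject's true level plus test error. When it is the only baseline information on that scale, part of the residual variance of the outcome is error in that one score. A second pre-dose rating reduces this part and has already been collected. The protocol uses this device for MMSE, which is only an adjustment variable, and does not state it for the scale being tested.

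ADAS-Cog 11 is the co-primary with the lower stated power (about 90%, against about 95% for ADCS-ADL in Section 11.2), and both endpoints must succeed. Precision is therefore most useful on this scale.

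Separately, without baseline-by-visit the model imposes the same relation between baseline and change at Week 12 as at Weeks 40 and 48, although the primary contrast rests on the last two visits only.

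**Working it through.** **Inputs from the protocol (Section 11.2).** "a total of 172 subjects per treatment group would provide approximately 90% power to detect a 2.5-point difference", "assuming a standard deviation of 7.1, respectively at a significance level (alpha) of 0.05 using a two-sided test".

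**Inputs assumed.** True between-subject baseline SD τ = 6 to 9; error SD of one assessment s = 2 to 4. The protocol gives neither.

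**Step 1: reproduce the plan's figure.** Power = Φ(δ / (SD·√(2/n)) − 1.96). With δ = 2.5, SD = 7.1 and n = 172, power is 90.4%, which matches the stated figure. At the final-analysis level of 0.0456 it is 89.7%.

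**Step 2: residual variance under each baseline choice.** Let 7.1² = 50.41 be the variance of change from Visit 2. The follow-up score then has variance 50.41 − s² given the true baseline.

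- Visit 2 score as covariate: τ²s²/(τ² + s²) + 50.41 − s².
- Both scores as covariates, or their mean used as baseline in both the change score and the covariate: τ²(s²/2)/(τ² + s²/2) + 50.41 − s².
- Change from Visit 2 with only the two-score mean as covariate: 50.41 − (s²/2)²/(τ² + s²/2).

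**Step 3: example with τ = 8, s = 3.**

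| Baseline handling | Residual variance | Power at 172 per arm |
|---|---|---|
| Visit 2 alone | 64·9/73 + 41.41 = 49.30 | 91.0% |
| Both scores (or mean in both places) | 64·4.5/68.5 + 41.41 = 45.61 | 93.0% |
| Change from Visit 2, mean alone as covariate | 50.41 − 20.25/68.5 = 50.11 | 90.6% |

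The third row is worse than the first. The Visit 2 error stays in the change score, and a covariate that is only half Visit 2 cannot remove it.

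**Step 4: range.** Comparing the second row with the first:

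| s | τ | Variance reduction | Power, Visit 2 alone → both |
|---|---|---|---|
| 2 | 6 | 3.4% | 90.6% → 91.6% |
| 2 | 9 | 3.7% | 90.5% → 91.5% |
| 3 | 6 | 6.6% | 91.4% → 93.1% |
| 3 | 9 | 7.7% | 90.9% → 92.9% |
| 4 | 6 | 10.0% | 93.0% → 95.2% |
| 4 | 9 | 12.7% | 91.8% → 94.9% |

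In subjects, 172 × (variance ratio − 1) runs from 172 × (50.01/48.30 − 1) ≈ 6 to 172 × (47.77/41.69 − 1) ≈ 25 per arm.

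**Step 5: a second parameterisation.** Here 7.1 is the residual SD with one baseline, observed baseline SD is 6 to 10 and test-retest reliability is 0.80 to 0.95 (also assumptions). The variance reduction is 1.7% to 14.1%, and power moves from 90.4% to between 90.9% and 94.1%.

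**Step 6: allowance for averaged MMSE in the model.** A simulation with baseline SD 8 and reliability 0.85 varied the assumed correlation of MMSE with true ADAS-Cog. At correlation 0 the residual SD fell from 7.084 to 6.818, a saving of 0.27. At correlation 0.8 it fell from 7.010 to 6.812, a saving of 0.20. MMSE recovers part of the gain, but most of it remains.

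The baseline-by-visit term was not quantified.

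**The case against.** The main objection is that the protocol never says the ADAS-Cog 11 baseline is a single value. A reader might infer from the text that the plan discards the screening score. The documents do not go that far. The reading rests on the contrast with the MMSE wording, and the SAP, which was not available for this review, may define baseline as Visit 2, the last pre-dose value or an average. That stands, and it is why the point is conditional.

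A reader might also call the unused score the strongest available predictor of the outcome. The protocol gives no correlation for any predictor, so this is unsupported.

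One covariate rule for both co-primaries is coherent, since ADCS-ADL cannot be averaged. MMSE also has a separate role in eligibility and stratification, so averaging it creates no obligation elsewhere. Both are fair defences of the plan, but neither is a reason to leave collected data unused.

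The size depends on assumed SDs, and the upper end needs s = 4. Allowing for an MMSE correlation of 0.6-0.8 reduces the gain to about 0.7-2.6 power points (1.0-1.9 at s = 3). The 25-subject figure is therefore too high as a practical expectation.

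Finally, omitting baseline-by-visit is a common modelling preference. Under randomisation a common slope does not bias the treatment contrast with complete data. That stands too; the term is a refinement.

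**Conclusion.** The point holds as a minor, free improvement. The protocol specifies two-score averaging for MMSE and leaves baseline ADAS-Cog 11 and CDR-SB undefined, although each has two pre-dose ratings. If Visit 2 alone is used, as the wording suggests, the plan gives up about 1-3 power points on ADAS-Cog 11 at 172 per arm, or somewhat less once averaged MMSE is counted. This rests on assumed values of τ and s and on equal, independent errors at the two pre-dose ratings.

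A reader might infer that the primary analysis is invalid or underpowered because of this. It is neither. There is no bias or type I error problem, and the stated 90% power reproduces without the second score. The gain reaches only one of the two final co-primary endpoints. The common baseline slope is stated in the protocol's model, but its effect here is unquantified.

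**What to change.** State which pre-dose ADAS-Cog 11 score or scores define baseline, separately for the change score and the covariate. Then take one of two routes:

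- keep change from Visit 2 and enter the Visit 2 and screening scores as two covariates; or
- use the two-score mean as baseline in both the change score and the covariate, which is equivalent when the two ratings have equal error.

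Do not combine change from Visit 2 with the mean as the only ADAS-Cog covariate. Apply the same rule to CDR-SB, at the interim and as a secondary endpoint. Keep the single Visit 2 baseline for ADCS-ADL. Add baseline-by-visit to the MMRM, for each pre-dose score that is entered.

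The cost is a sentence of definition and a changed model line, fixed before unblinding. No new data, visits or sample size change are needed.

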#### **11.3.2.1.1 Sensitivity Analyses**

The following sensitivity analyses will be performed on each of the co-primary endpoints:

- Repeat above analysis using the PP population.
- Impute missing values using a last z-score carried forward method (converted back to the original scale) and analyze the primary endpoint (Average of Weeks 40 and 48 only) using analysis of covariance (ANCOVA) with fixed effects of treatment group, ApoE4 status, acetylcholinesterase inhibitor and/or memantine usage, site/country and baseline MMSE with baseline score as a covariate.
- Pattern mixture model:  
The pattern-mixture model approach uses a control-based pattern imputation ([Ratitch and O'Kelly, 2011](#)). With this approach, subjects who discontinued from the COR388 HCl 80 mg or COR388 HCl 40mg treatment group will be assumed to follow a similar outcome trajectory as subjects from the placebo (control) arm and subjects who discontinued from placebo (control) treatment are modeled as completers within their own arm (MAR within control arm). That is, the imputation model for the missing observations in the active treatment groups are constructed not from the observed data in the corresponding active treatment group but rather from the observed data in the placebo treatment group. This model is also the imputation model that will be used to impute missing observations in the placebo treatment group. This will

be implemented by utilizing the MONOTONE REG statement of SAS® PROC MI with the option nimpute=5.

Pattern mixture model tends to overestimate the already very large variability in Alzheimer's disease data, these model results are likely to be much less able to discriminate treatment differences than the primary model. The results of this imputation method will primarily be used to assess the potential bias of the main model estimates due to dropout by comparing the estimates between the primary and sensitivity models.

Additional subgroups including gender, demographic, and other baseline characteristics may be performed. Further details will be given in the SAP.

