### **11.3 Final Analysis**

#### **11.3.1 Analysis Populations**

- **Intent-To-Treat Population (ITT):** The ITT population will include all subjects who are randomized regardless of whether or not they took study drug. This population will serve as the basis for all efficacy analyses. When change from baseline is assessed, subjects will be included in the analysis only if both a baseline and a postbaseline measure are available.
- **The Per Protocol population (PP):** The PP population will include all ITT subjects who do not have any major protocol deviations that would affect efficacy (e.g., <80% treatment compliance, taking a prohibited medication). Major protocol deviations will be reviewed and determined prior to unblinding. The PP population will be used for supportive sensitivity analyses.
- **Safety Population:** The Safety population will include all subjects who receive at least one dose of study drug. Safety analyses will be performed using the Safety population, and subjects will be analyzed according to the treatment they actually receive.

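### Fixing the control-based sensitivity analysis at 5 imputations leaves avoidable seed noise, about 40–60% of the small gap it is meant to show

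*Protocol*

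**What the plan says.** Protocol Section 11.3.2.1.1 lists a control-based pattern-mixture model among the sensitivity analyses of both co-primary endpoints. In it, "subjects who discontinued from the COR388 HCl 80 mg or COR388 HCl 40mg treatment group will be assumed to follow a similar outcome trajectory as" placebo subjects. Missing values in the active arms are therefore drawn from a model fitted to placebo data. The software setting is fixed: "PROC MI with the option nimpute=5".

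The same section says what the analysis is for. It expects little from it as a test: "these model results are likely to be much less able to discriminate treatment differences than the primary model". Instead, its output is to "primarily be used to assess the potential bias of the main model estimates due to dropout by comparing the estimates between the primary and sensitivity" analyses.

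Two other sections bear on the size of the issue. Section 11.2 plans the sample size "assuming approximately 10% will drop out prior to 48 weeks". Section 11.3.1 says that, when change from baseline is assessed, "subjects will be included in the analysis only if both a baseline and a postbaseline measure are available".

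**The concern.** The quantity to be read is a difference between two estimates computed from the same subjects. Most of their sampling error cancels in that difference. The noise from the imputation draws does not, because only one of the two estimates carries it. A number of imputations that is adequate for a p-value or a confidence interval can therefore be too small for this comparison.

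If the gap is small and the seed noise is of similar order, the reader may see no gap, or one twice the expected size, only because of the seed. The comparison is made for two doses on two co-primary endpoints, so it is read four times. At stake is the interpretation of a supportive analysis, not the trial's primary conclusion.

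**Working it through.** **Inputs from the protocol.** Section 11.2: 191 per arm, 10% dropout, 172 completers per arm; ADAS-Cog 11 effect 2.5 and SD 7.1; ADCS-ADL effect 3.9 and SD 10.5; two-sided alpha 0.05. Section 11.3.2.1: endpoint is the "mean change from baseline in ADAS-Cog 11 at the end of the study (average of Weeks 40 and 48"), and likewise for ADCS-ADL. Table 1: post-baseline efficacy visits in the treatment period at Weeks 12, 24, 40 and 48. Section 11.3.2.1.1: m = 5 imputations.

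**Assumptions (not in the protocol).** Effect linear in time, equal dropout in both arms, dropout time uniform, five within-subject covariance structures.

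**1. The plan's own figure.** SE = 7.1 × √(2/172) = 0.766, and 2.5/0.766 = 3.265. Power = Φ(3.265 − 1.960) = 0.904, against the stated approximately 90%. Also 191 × 0.90 = 171.9, so the stated 172 is reproduced.

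**2. Hand check of the orders of magnitude.** About 19 subjects per arm drop out. If every dropout lost all benefit, the gap would be about 0.10 × 2.5 = 0.25 points. It will be smaller, because benefit seen before dropout carries into the imputed values. For the noise, assume a conditional residual SD of 4–5.5 points. One imputation then adds an SD of √2 × √19 × (4 to 5.5)/191 = 0.13–0.18. Dividing by √5 gives 0.06–0.08.

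**3. Simulation.** 250 trials with 100 imputations each per scenario, one dose against placebo. The gap is the missing-at-random (MAR) estimate minus the control-based estimate. The seed SD with m imputations is √(B/m), where B is the between-imputation variance. The last column is the chance that the seed alone moves the gap by at least its expected size, 2Φ(−gap/seed SD). It is not clear whether the post-baseline rule in Section 11.3.1 applies to the imputed analysis, so both readings were run. ADAS-Cog 11, 10% dropout, m = 5:

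| Covariance structure | Gap | Seed SD | Ratio | Chance |
|---|---|---|---|---|
| *No post-baseline score: left out* | | | | |
| Slope plus noise | 0.098 | 0.058 | 0.59 | 0.089 |
| CS 0.6, growing SD | 0.110 | 0.052 | 0.47 | 0.035 |
| AR 0.8, growing SD | 0.093 | 0.058 | 0.62 | 0.109 |
| CS 0.5, constant SD | 0.122 | 0.057 | 0.47 | 0.032 |
| CS 0.7, growing SD | 0.095 | 0.046 | 0.49 | 0.040 |
| *All randomised imputed* | | | | |
| Slope plus noise | 0.155 | 0.072 | 0.47 | 0.033 |
| CS 0.6, growing SD | 0.159 | 0.067 | 0.42 | 0.017 |
| AR 0.8, growing SD | 0.154 | 0.076 | 0.49 | 0.042 |
| CS 0.5, constant SD | 0.168 | 0.072 | 0.43 | 0.019 |
| CS 0.7, growing SD | 0.157 | 0.065 | 0.41 | 0.015 |

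The ratio must be read row by row. The largest seed SD does not occur with the smallest gap.

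**4. Other settings, m = 5.**
- ADAS-Cog 11, 20% dropout: seed SD 0.067–0.106, gap 0.19–0.36, ratio 29–45%, chance under 3%.
- ADCS-ADL, 10% dropout: seed SD 0.069–0.112, gap 0.15–0.27, ratio 39–57%, chance 1–8%. At 20% dropout the ratio is 28–42%.
- A separate simulation for ADAS-Cog 11 at 10% dropout, with correlations 0.5–0.8 and early to very late dropout, gave seed SD 0.036–0.080, gap 0.07–0.21 and ratio 32–67%. A third gave a ratio of 43–71%.

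**5. Scale against the trial's precision.** The SE of the effect in the main simulation is 0.62–0.72. The seed SD is 7.5–11.3% of it, so its share of the combined variance is 0.075² to 0.113², or 0.6–1.3%.

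**6. Effect of more imputations.** Seed SD scales as 1/√m, so moving from 5 to 100 multiplies it by √(5/100) = 0.224. The ratio of 41–62% becomes 9–14%. The gap has its own sampling SD of 0.039–0.064, which no number of imputations removes. The total SD of the observed gap falls from 0.061–0.098 to 0.041–0.066, a reduction r of 31–39%. Because B/100 is one twentieth of B/5, the share of the gap's variance due to the seed with m = 5 is [1 − (1 − r)²]/0.95. That is (1 − 0.476)/0.95 = 55% to (1 − 0.372)/0.95 = 66%. With five imputations, more than half of the variance of the observed gap is seed noise.

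**The case against.** The strongest reply is that nothing of consequence changes. Five imputations are valid under Rubin's rules, and the noise is small beside the effect and its SE. Even in the scenario with the largest seed SD, 95% of seeds give a gap of 0.154 ± 1.96 × 0.076, or about 0.005 to 0.30 points. The upper end is 12% of the 2.5-point effect. A reader at either extreme would conclude that dropout bias is small. The problem also shrinks where the gap is larger: at 20% dropout the chance of a misleading shift is under 3%. All of this stands, and it is why the point carries low weight.

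It can also be said that comparing estimates does not exclude reading them with their standard errors. That is true. But each estimate's SE is roughly ten times the sampling SD of the gap, so it says little about a paired difference.

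Section 11.1 allows the SAP to record deviations from the protocol's analyses, so the number may change there. That does not alter the number the protocol states.

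Finally, 100 is not a derived threshold. Twenty imputations would halve the seed SD, to about 20–31% of the gap, and 50 would bring it to about 13–20%. That is fair: 100 is one reasonable choice, preferred because the extra draws cost almost nothing.

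**Conclusion.** The concern holds, at low weight. For the use the protocol gives this analysis, five imputations are too few. The seed SD is about 0.05–0.08 ADAS-Cog 11 points against an expected gap of about 0.09–0.17, with a ratio of 41–62% in the main simulation and 32–71% across all simulations at 10% dropout. For ADAS-Cog 11, about 2–11% of seeds would make the gap look absent or at least doubled.

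These figures rest on assumed visit correlations, dropout timing, a linear effect and equal dropout. The MAR comparator stands in for the planned MMRM and omits its site/country, baseline MMSE, ApoE4 and background-therapy terms. The exact values would move with these choices. That seed noise is a large share of the gap did not change in any structure tried.

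**What to change.** In the sentence of Section 11.3.2.1.1 that sets the number of imputations, replace 5 with at least 100. The random seed can be left to the SAP.

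The cost is one number in one sentence and negligible computing time. Conduct, sample size, alpha and the primary analysis are untouched. The change does not make the gap exact: with 100 imputations its total SD is still 33–47% of its expected size, down from 52–77%, and what remains is almost all sampling variation.
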